7.2.3.1.1. Olaratumab

7.2.3.1.1.1. Infusion-Related Reactions

As with other therapeutic protein products, hypersensitivity reactions may occur during or following olaratumab administration.

For the initial 2 cycles of olaratumab treatment, it is mandatory that patients be closely monitored by the medical staff for signs and symptoms indicative of an IRR from the start of the infusion until at least 1 hour after the end of the infusion (see [Table JGDM.1](#)) in an area where emergency medical resuscitation equipment and other agents (such as epinephrine or prednisolone equivalents) are available. If no evidence of an IRR manifests during the initial 2 cycles of olaratumab, then no observation period is required for subsequent treatment cycles. In the event an IRR occurs thereafter, then the 1-hour observation period should be reinstated (see Section 7.1.2).

Olaratumab IRRs will be defined according to the NCI-CTCAE Version 4.0 definition of IRRs.

Symptoms occurring during or following infusion of investigational therapy may also be defined according to AE terms such as allergic reaction, anaphylaxis, or cytokine release syndrome (NCI-CTCAE Version 4.0 section “Immune system disorders”). In the setting of symptoms occurring during or following infusion of investigational therapy, investigators are encouraged to use the AE term “IRR” and any additional terms (including those not listed here) that best describe the event.

For patients who experience a Grade 1 or 2 IRR, the infusion should be stopped and the patient treated with the following (or equivalent) medications: a histamine H1 antagonist (for example, diphenhydramine) and glucocorticoid (for example, dexamethasone) IV, acetaminophen, and oxygen (as indicated), according to standard medical practices. After recovery, the infusion rate should be decreased by 50% for the duration of the infusion. After a Grade 1 or 2 IRR, patients should be premedicated with the following (or equivalent) medications: a histamine H1 antagonist (for example, diphenhydramine) and glucocorticoid (for example, dexamethasone) IV, and acetaminophen, as appropriate, approximately 30-60 minutes prior to all subsequent olaratumab infusions.

A Grade 3 or 4 IRR will require immediate treatment, including the use of epinephrine, bronchodilators, and/or glucocorticoids for symptomatic bronchospasm, IV fluids and/or pressors for hypotension, and immediate and permanent discontinuation of olaratumab with appropriate supportive care.

If a patient experiences an IRR to olaratumab, all attempts should be made to obtain an anti-olaratumab antibody blood sample as close to the onset of the event as possible, at the resolution of the event, and 30 days (± 3 days) following the event. In addition, these same samples may be assessed for levels of olaratumab and for pharmacodynamic markers to provide information on the nature of the IRR. The procedure for sample collection and handling is described in a separate procedural manual.

Section 7.1.3 provides information on doxorubicin and IRRs.

7.2.3.1.1.2. Hematologic Toxicity

Table JGDM.2 summarizes the olaratumab dose modifications required in case of hematological toxicities.

Table JGDM.2. General Guidelines for Olaratumab Dose Modification Due to Hematologic Toxicity Deemed Related to Olaratumab

Toxicity	Required Dose Modification
Neutropenia	
ANC Grade 1-3	No dose modification required.
ANC <500 cells/ μ L (Grade ≥ 4)	No treatment administered; treatment cycle delayed.
At retreatment:	
If Grade ≥ 3 neutropenic fever/infection has occurred	Withhold dose until ANC is 1000 cells/ μ L or higher; reduce dose to 12 mg/kg (15 mg/kg if toxicity occurs during Cycle 1 or Cycle 2).
If Grade 4 neutropenia lasting longer than 1 week has occurred	Withhold dose until ANC is 1000 cells/ μ L or higher; reduce dose to 12 mg/kg (15 mg/kg if toxicity occurs during Cycle 1 or Cycle 2).
Grade 4 ANC without fever/infection	Retreatment with olaratumab at full dose at investigator's discretion with recommended use of prophylactic G-CSFs.
Second incidence of either: 1) Grade ≥ 3 neutropenic fever/infection 2) Grade 4 neutropenia lasting longer than 1 week	Second dose reduction to 10 mg/kg.
Thrombocytopenia	
Platelets <75,000 cells/ μ L (Grade 1)	No treatment administered; treatment delayed until resolved to $\geq 100,000$ cells/ μ L.
Anemia	
Hemoglobin <9 gm/dL (Grade 2)	No treatment administered; treatment delayed until resolved to \leq Grade 1.

Abbreviations: ANC = absolute neutrophil count; G-CSF = granulocyte colony-stimulating factor.

7.2.3.1.1.3. Nonhematologic Toxicity

Specific guidelines for dose adjustments in patients who experience olaratumab IRRs may be found in Section 7.2.3.1.1.1.

Table JGDM.3 provides general guidelines for dose modification for other nonhematologic toxicities related to olaratumab. If more than 2 toxicity-related olaratumab dose reductions are required, treatment with this agent will be permanently discontinued.

Table JGDM.3. General Guidelines for Olaratumab Dose Modification Due to Nonhematologic Toxicity Deemed Related to Olaratumab

Reaction Grade	Required Dose Modification
Grade 1	No dose modification is required.
Grade 2	At the investigator's discretion, the patient may continue to receive olaratumab per protocol, provided that the event does not pose a serious health risk or is easily treated.
Grade 3	For a Grade 3 toxicity not adequately controlled with appropriate supportive care, the dose must be withheld until toxicity is Grade ≤ 1 or has returned to pretreatment baseline; then treatment may resume at a reduced dose of 12 mg/kg (15 mg/kg if the toxicity occurs during Cycle 1 or Cycle 2). If toxicity recurs after therapy resumes, a second dose reduction (to 10 mg/kg) is permitted.
Grade 4	The dose must be withheld until dose toxicity is \leq Grade 1 or has returned to baseline. Permanent discontinuation should be considered for any patient experiencing Grade 4 nonhematological toxicity assessed as related to olaratumab. However, if resumption of dosing is deemed appropriate by the investigator, treatment may resume only after consultation with the Lilly study physician, with the dose reduced to 10 mg/kg (15 mg/kg if the toxicity occurs during Cycle 1 or Cycle 2). If Grade 4 toxicity recurs after therapy resumes, olaratumab treatment will be discontinued.

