Any patient who requires a dose reduction will continue to receive the reduced dose for the remainder of the study. Any patient who has had 2 dose reductions and who experiences a toxicity that would cause a third dose reduction must be discontinued from study drug.

In the event of an alteration in olaratumab dose due to an olaratumab-related toxicity, doxorubicin need not be altered, and the planned doxorubicin schedule should be maintained.

Similarly, olaratumab therapy need not be altered for doxorubicin-related toxicity. An alteration in doxorubicin dose will always necessitate a corresponding change to dexrazoxane, if administered, in order to maintain a dosage ratio of 10:1 (dexrazoxane:doxorubicin).

Discontinuations:

In general, discontinuation of olaratumab will not necessitate discontinuation of doxorubicin. In the event of discontinuation of olaratumab therapy due to an olaratumab-related toxicity or Grade 3 or 4 IRR, doxorubicin need not be altered, and the planned doxorubicin schedule may be maintained at the discretion of the investigator. Discontinuation of doxorubicin will necessitate discontinuation of olaratumab.

Any changes in treatments being added to or removed from patient care will be recorded on the eCRF.

The following information (in this section and the following subsections) pertains to dose modifications and delays for and management of AEs of concern, which may or may not be associated with olaratumab therapy, including the following:

- IRR (see Section 7.2.3.1.1.1)
- Hematologic toxicity (see Section 7.2.3.1.1.2)
- Nonhematologic toxicity (see Section 7.2.3.1.1.3)

The following information (in this section and the following subsections) pertains to dose modifications and delays for and management of AEs of concern, which may or may not be associated with doxorubicin therapy, including the following:

- Hematologic toxicity (see Section 7.2.3.1.2.1)
- Cardiovascular toxicity (see Section 7.2.3.1.2.2)
- Hepatic impairment (see Section 7.2.3.1.2.3)
- Nonhematologic toxicity (Section 7.2.3.1.2.4)

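### Tables JGDM.2 and JGDM.3 set the olaratumab dose without reference to the dose being given, so a second related toxicity of the other type can bring a reduction that leaves the dose unchanged

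*Protocol*

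**What the plan says.** The planned olaratumab dose is 20 mg/kg on Days 1 and 8 of Cycles 1 and 2, then 15 mg/kg on Days 1 and 8 of Cycles 3 to 7 (protocol Sections 5.4 and 6.2).

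Two tables govern reductions for toxicity attributed to olaratumab. Table JGDM.2 (Section 7.2.3.1.1.2) is titled "General Guidelines for Olaratumab Dose Modification Due to Hematologic Toxicity Deemed Related to Olaratumab". It covers Grade 3 or worse neutropenic fever or infection, and Grade 4 neutropenia lasting more than a week. The first such event leads to "reduce dose to 12 mg/kg (15 mg/kg if toxicity occurs during Cycle 1 or Cycle 2"). A second incidence of either leads to "Second dose reduction to 10 mg/kg".

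Table JGDM.3 (Section 7.2.3.1.1.3) covers nonhematologic toxicity:

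- Grade 3 not controlled by supportive care: the dose is withheld, "then treatment may resume at a reduced dose of 12 mg/kg (15 mg/kg if the toxicity occurs during Cycle 1 or Cycle 2"). On recurrence, "If toxicity recurs after therapy resumes, a second dose reduction (to 10 mg/kg) is permitted".
- Grade 4: dosing may resume only after consultation with the sponsor's physician, "with the dose reduced to 10 mg/kg (15 mg/kg if the toxicity occurs during Cycle 1 or Cycle 2").

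Two general rules sit alongside. Section 7.2.3.1 states: "Any patient who requires a dose reduction will continue to receive the reduced dose for the remainder of the study". On the number of reductions, Section 7.2.3.1.1.3 states: "If more than 2 toxicity-related olaratumab dose reductions are required, treatment with this agent will be permanently discontinued". Section 7.2.3.1 has a matching cap of two. Neither cap separates hematologic from nonhematologic events.

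**The concern.** The rows choose a dose from toxicity type, grade, cycle and whether the same type has occurred before. The cycle condition stands in for the planned dose, but it does not track a dose that has already been cut. A patient with one neutropenic event and then a first nonhematologic event (or the reverse) is a first-event case in the second table, although this is that patient's second olaratumab-related toxicity.

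Two things follow. Read row by row, the instruction can be to resume the dose at which the second toxicity arose. And because the caps give a stopping point but no dose, and do not say whether an unchanged dose counts as a reduction, sites may dose and count the same patient differently. SAP Section 5.3.4 takes the number of dose reductions as reported in the eCRF, so inconsistent counting would reach the exposure summaries.

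**Working it through.** The plan states no figure to reproduce. The check applies the rows as written.

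**Inputs.** First-event dose by row (Tables JGDM.2 and JGDM.3):

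| Event | Cycles 1-2 | Cycles 3-7 |
|---|---|---|
| N: qualifying neutropenic event | 15 mg/kg | 12 mg/kg |
| G3: Grade 3 nonhematologic | 15 mg/kg | 12 mg/kg |
| G4: Grade 4 nonhematologic | 15 mg/kg | 10 mg/kg |

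The four mixed sequences are N then G3, N then G4, G3 then N, and G4 then N. The two events are placed in different cycles i < j. Each event is taken to occur after Day 8 of its cycle, with dosing resumed at the named dose.

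**Dose at the second event**

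| Sequence | Both in Cycles 1-2 | Cycles 1-2, then 3 or later | Both in Cycle 3 or later |
|---|---|---|---|
| N then G3 | 15 to 15 | 15 to 12 | 12 to 12 |
| G3 then N | 15 to 15 | 15 to 12 | 12 to 12 |
| N then G4 | 15 to 15 | 15 to 10 | 12 to 10 |
| G4 then N | 15 to 15 | 15 to 12 | at 10, row names 12 |

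For comparison, two neutropenic events in the same cycles go to 10 mg/kg (15 to 10, or 12 to 10).

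**Counts.** A second event after Day 8 of Cycle 7 has no later olaratumab dose to change, so j runs from 2 to 6.

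- Cycle pairs: both in 1-2, 1; 1-2 then 3-6, 2 × 4 = 8; both in 3-6, 6. Total 15, and 15 × 4 sequences = 60.
- Unchanged: 4 × 1 (15 to 15) + 2 × 6 (12 to 12) = 16.
- Lowered: 4 × 8 + 1 × 6 = 38.
- Row above current dose: 1 × 6 = 6.
- Check: 16 + 38 + 6 = 60.

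Including Cycle 7 second events would add 6 pairs, or 24 sequences (8 unchanged, 12 lowered, 4 with the row above the current dose), giving 24, 50 and 10 of 84. Those 24 have no effect on dosing under the stated timing.

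**Exposure in two examples.** Planned total: 4 × 20 + 10 × 15 = 230 mg/kg.

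- 15 to 15, events after Day 8 of Cycles 1 and 2. By the row: 2 × 20 + 2 × 15 + 10 × 15 = 220 (220/230 = 96%). With 10 mg/kg from Cycle 3: 2 × 20 + 2 × 15 + 10 × 10 = 170 (74%). By the row, Cycles 3-7 deliver 150 mg/kg, the same as for a patient with no toxicity.
- 12 to 12, events after Day 8 of Cycles 3 and 4. By the row: 4 × 20 + 2 × 15 + 2 × 12 + 6 × 12 = 206 (90%). With 10 mg/kg from Cycle 5: 4 × 20 + 2 × 15 + 2 × 12 + 6 × 10 = 194 (84%).

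**The case against.** The best defence is that the protocol can be read coherently. Reductions are capped at two without regard to type, both tables call the second reduction 10 mg/kg, and a move from 15 to 15 is not a reduction. An investigator who counts reductions arrives at 10. The tables are also labelled general guidelines. This has weight, but the inference is never stated for mixed events. The tables' action column is headed as required, and the matching row names 15 or 12.

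Several other points stand and limit the finding:

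- A reader might infer that 10 mg/kg is reachable as a second step only through a same-type repeat. It is not: a Grade 4 nonhematologic event in Cycles 3-7 takes a patient at 15 or 12 mg/kg to 10.
- A reader might infer that a patient already at 10 mg/kg would be raised to 12, or has no instruction. Section 7.2.3.1 keeps the reduced dose for the rest of the study, so the patient stays at 10 once the withholding conditions are met.
- Resumption is not automatic. The Grade 3 row permits it; the Grade 4 row asks that permanent discontinuation be considered and requires the sponsor's physician to be consulted. The investigator may stop study drug at any time (Section 6.3.2).
- Olaratumab need not change for doxorubicin-related toxicity (Section 7.2.3.1), so both events must be attributed to olaratumab. The 15-to-15 case also needs a qualifying event in monotherapy Cycle 1, and Section 5.4 reports no dose-limiting toxicity with single-agent olaratumab in the earlier studies.

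Against dismissing mixed events altogether, Section 5.4 reports more neutropenia and more mucositis with olaratumab plus doxorubicin than with doxorubicin alone, one toxicity from each table's domain.

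**Conclusion.** The point holds as a minor dosing-safety clarification. In two settings the literal rule for a second, other-type toxicity does not lower the dose: any mixed pair in Cycles 1-2 (15 to 15 mg/kg), and a neutropenic plus a Grade 3 nonhematologic event in Cycles 3-7 (12 to 12 mg/kg). A patient with two neutropenic events in the same cycles would get 10 mg/kg; the plan gives no reason for the difference. The remaining mixed steps lower the dose as they should, apart from the 6 sequences in which the patient is held at 10 mg/kg.

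The figure of 16 in 60 might be read as a risk. It is not: it gives every cycle pair and sequence equal weight, and the documents contain no rate of qualifying olaratumab-attributed events from which to estimate affected patients among the approximately 35 enrolled. Harm should be rare and limited, given the withholding rules, the two-reduction cap, and the fact that 15 mg/kg is the planned Cycle 3-7 dose. Nor does the point touch the primary analysis: in these sequences the second event falls in Cycle 2 at the earliest, after the post-monotherapy biopsy and the Cycle 2 Day 1 predose blood sample.

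**What to change.** Add to Section 7.2.3.1:

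> Olaratumab reductions are counted across hematologic and nonhematologic toxicities. If the dose named in Table JGDM.2 or JGDM.3 is not lower than the patient's current dose, give the second dose reduction, to 10 mg/kg, instead; no table entry raises a reduced dose.

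Applied to the 60 sequences, 38 keep their table dose, 16 go to 10 mg/kg (4 from 15, 12 from 12), and 6 stay at 10 mg/kg. No mandatory stop at 10 mg/kg after a single reduction is proposed. That would be stricter than the two-reduction cap, so the case is better left to the existing keep-the-reduced-dose rule and discussion with the sponsor's physician.

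One trade-off should be acknowledged. A second neutropenic or Grade 3 event of the other type would take a patient from 15 to 10 mg/kg in Cycle 2 but from 15 to 12 mg/kg in Cycle 3. The 15-to-10 step matches what a repeat neutropenic event already brings. A 15-12-10 ladder would remove the unevenness, but would alter steps the tables already define for same-type repeats.

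The cost is one short paragraph in an amendment or site clarification, with no added visits, procedures or patients. The downside is slightly less olaratumab in the few patients affected.

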7.2.3. Dose Modifications

7.2.3.1. Dose Delays, Modifications, and Discontinuations

After treatment has been initiated, in order to start the next cycle, the following criteria must be fulfilled:

- ANC $\geq 1.0 \times 10^3/\mu\text{L}$ (1000/ μL ; $\geq 1.0 \times 10^9/\text{L}$)

Note that in order to administer single-agent olaratumab on Day 8, ANC must be $\geq 750/\mu\text{L}$; $\geq 0.75 \times 10^9/\text{L}$. If the ANC is $< 750/\mu\text{L}$, the Day 8 administration of olaratumab may be delayed for a maximum of 7 days. If the ANC level has not increased to $\geq 750/\mu\text{L}$ within 7 days, then the Day 8 olaratumab dose in that cycle should be skipped and dosing resumed on Day 1 of the following cycle if criteria for dosing are met. If all dosing criteria are met, a delay or omission of the Day 8 olaratumab dose should not result in a delay of the Day 1 olaratumab dose of the following cycle.

- Platelets $\geq 100 \times 10^3/\mu\text{L}$ (100,000/ μL ; $\geq 100 \times 10^9/\text{L}$)
- Hemoglobin ≥ 8 g/dL
- Creatinine clearance ≥ 45 mL/min (refer to [Attachment 7](#) for the Cockcroft-Gault formula)
- Proteinuria ≤ 1000 mg in 24 hours (if routine urinalysis indicates $\geq 2+$ proteinuria) (to be performed every other cycle)

- Total bilirubin below ULN
- AST and ALT $\leq 3.0 \times$ ULN, or $\leq 5 \times$ ULN if the transaminase elevation is due to liver metastases
- Olaratumab-related AEs that are NCI-CTCAE Version 4.0 Grade <2 or equivalent severity to baseline

Delays:

In general, dose delays of 1 study drug (olaratumab or doxorubicin) due to toxicity guidances outlined in Sections 7.2.3.1.1 and 7.2.3.1.2 will not necessitate delays of the other study drug.

Treatment may be delayed for up to 21 days (1 equivalent cycle) to allow a patient sufficient time for recovery from study drug-related toxicity. If a patient does not recover from the toxicity within 42 days (2 equivalent cycles) from Day 1 of the previous treatment cycle, then the patient must be discontinued from study therapy.

Any procedure or sample collection whose timing is related to olaratumab dosing is to be completed according to when the olaratumab dose was actually administered, not when that dose was expected to occur. Samples whose adjusted timing would fall outside of the treatment cycle duration due to dose delay may be omitted.

Dose Modifications:

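### Table JGDM.2 both requires an olaratumab dose reduction and permits full-dose retreatment after the same event: Grade 4 neutropenia of more than a week without fever or infection

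*Protocol*

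**What the plan says.** Table JGDM.2 (Protocol 7.2.3.1.1.2) applies only to hematologic toxicity attributed to olaratumab. It holds treatment while the ANC is below 500/µL and then lists what to do at retreatment:

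- **Prolonged neutropenia.** "If Grade 4 neutropenia lasting longer than 1 week has occurred": withhold until the ANC is back to 1000/µL, then "reduce dose to 12 mg/kg (15 mg/kg if toxicity occurs during Cycle 1 or Cycle 2"). The row has no fever condition.
- **Fever or infection.** If Grade 3 or higher "neutropenic fever/infection has occurred", the action is the same.
- **No fever or infection.** "Grade 4 ANC without fever/infection": "Retreatment with olaratumab at full dose" is left to the investigator, with prophylactic G-CSF recommended. The row has no duration condition.
- **Second incidence** of either of the first two events: "Second dose reduction to 10 mg/kg".

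The only prose in that section is one sentence introducing the table.

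The general rules are in Protocol 7.2.3.1. Under "After treatment has been initiated, in order to start the next cycle, the following criteria must be fulfilled" the ANC must be at least 1000/µL. For Day 8 it must be at least 750/µL; otherwise "the Day 8 administration of olaratumab may be delayed for a maximum of 7 days", after which the dose is skipped. A reduced dose is kept for the rest of the study, and a toxicity calling for a third reduction means discontinuation.

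**The concern.** The two rows prescribe different doses of the investigational drug after the same event. An investigator who reads down the table can justify either one. Three things depend on the choice:

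- **Dose at retreatment.** A site following the full-dose row skips a reduction that the row above requires after prolonged Grade 4 neutropenia.
- **Count of reductions.** Two patients with the same history can stand at zero and at one of the two permitted reductions. This holds even where the next dose is the same. A patient retreated at full dose who has a second prolonged episode would also face a second reduction, to 10 mg/kg, without having had a first.
- **Records.** SAP 5.8 summarizes reductions and SAP 5.6 names dosing errors among the important protocol deviations. As written, full-dose retreatment here is both permitted and a missed required reduction.

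This is not about re-dosing during Grade 4 neutropenia, because the ANC thresholds in 7.2.3.1 apply under either row.

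**Working it through.** The plan gives no figure to reproduce. The check has two parts: matching the rows to the possible events, and working out the dose difference.

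**1. Row matching.** Cross fever/infection (none, below Grade 3, Grade 3 or higher) with duration of Grade 4 neutropenia (1 week or less, more than 1 week). This gives 3 × 2 = 6 states for a first episode.

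| Fever/infection | 1 week or less | More than 1 week |
|---|---|---|
| None | full dose at discretion | **reduce, and full dose at discretion** |
| Below Grade 3 | no row | reduce |
| Grade 3 or higher | reduce | reduce |

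One state conflicts and one is uncovered.

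**2. Search for a rule that ranks the rows.** Section 7.2.3.1 covers cycle-start criteria, delays, the limit on reductions and the keeping of a reduced dose. None of this ranks the rows. The amendment summary in the protocol and the SAP give no rule on the point either. Doxorubicin Table JGDM.4 has the same pair of overlapping rows, but the text of 7.2.3.1.2.1 settles it: reduce for an afebrile Grade 4 episode of more than a week, and keep full dose only for one of less than a week. That text names doxorubicin only.

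**3. Dose difference over later cycles.** Inputs are the planned doses in Protocol 6.2 (20 mg/kg in Cycles 1 and 2, 15 mg/kg in Cycles 3 to 7, two doses per cycle) and the reduced levels in Table JGDM.2. Full dose is read as the dose planned for each later cycle, all doses are given, and a reduced dose is kept to the end.

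| Episode in cycle | Full-dose row (mg/kg) | Reduction row (mg/kg) | Difference |
|---|---|---|---|
| 1 | 2×20 + 10×15 = 190 | 12×15 = 180 | 10 |
| 2 | 10×15 = 150 | 10×15 = 150 | 0 |
| 3 | 8×15 = 120 | 8×12 = 96 | 24 |
| 4 | 6×15 = 90 | 6×12 = 72 | 18 |
| 5 | 4×15 = 60 | 4×12 = 48 | 12 |
| 6 | 2×15 = 30 | 2×12 = 24 | 6 |
| 7 | 0 | 0 | 0 |

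Per dose, the gap after Cycles 3 to 6 is (15 − 12)/15 = 20%. After Cycle 1 it is 20 versus 15 mg/kg, for the two Cycle 2 doses only.

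**4. If a delayed Day 8 dose of the same cycle is still given.** Add 20 − 15 = 5 mg/kg in Cycles 1 and 2, and 15 − 12 = 3 mg/kg in Cycles 3 to 7. The differences become 15, 5, 27, 21, 15, 9 and 3 mg/kg for Cycles 1 to 7. The delay is limited to 7 days (Day 8 + 7 = Day 15), so this needs onset before Day 8 and recovery by about Day 15. It also takes the ANC as back to 1000/µL, so that both rows allow the dose.

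**The case against.** The strongest reply is that one row is a requirement and the other a permission. An investigator who reduces complies with both; one who gives full dose breaches the row that names the duration. The rest of the table supports this. If the full-dose row governed every episode free of fever and infection, the prolonged-neutropenia row would add only the case of fever or infection below Grade 3. The second-incidence row also presupposes that the first prolonged episode led to a reduction, and the doxorubicin text follows the same scheme.

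This establishes the intent, and reduction is the better reading. It does not supply a rule: the full-dose row still grants discretion for an event that it literally covers, and the text that settles the matter for doxorubicin was not written for olaratumab. The table's title calls it general guidelines, but its column is headed as required modifications.

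The reply on weight largely stands. The event must be Grade 4, last more than a week, come without fever or infection, and be attributed to olaratumab. One state in six is a count of logical cells, not a risk. The later-cycle difference is zero after Cycles 2 and 7, and the Day 8 series applies only under the timing in step 4. The ANC thresholds, the G-CSF recommendation and the sponsor's safety monitoring limit the harm. Against that, Protocol 5.4 reports more neutropenia with olaratumab plus doxorubicin than with doxorubicin alone, so the setting is not remote.

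**Conclusion.** The concern holds. Table JGDM.2 gives two incompatible instructions for one of six first-episode states, and no text for olaratumab says which applies. The consequence is a dose level of 20 versus 15 mg/kg at the next cycle after a Cycle 1 episode, and 15 versus 12 mg/kg after Cycles 3 to 6. Over all later cycles the difference is at most 24 mg/kg, or 27 mg/kg with a delayed Day 8 dose, both for a Cycle 3 episode. The count toward discontinuation can also differ.

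These figures rest on reading full dose as the planned dose for each later cycle, on all later doses being given, and on the reduced dose being kept. How often the event would occur cannot be judged from the documents. The primary biomarker analysis and the sample size do not depend on it. It should be corrected because it is a contradiction in a safety dosing rule for the investigational drug, although the affected state is narrow.

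**What to change.** In the next amendment, add a duration limit to the full-dose row of Table JGDM.2, so that it reads "Grade 4 ANC without fever/infection" followed by *lasting 1 week or less*. This complements the prolonged-neutropenia row exactly and takes the conflicting states from 1 to 0. It matches the sponsor's doxorubicin rule except at exactly 1 week, which the doxorubicin text leaves open.

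The change does not cover Grade 4 neutropenia of 1 week or less with fever or infection below Grade 3, which meets no retreatment row before or after. The doxorubicin text and Table JGDM.4 are not part of this defect.

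The cost is one phrase in one row, with no change to procedures, sample size or analysis.
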